### **RBC $\leq$ 21 Day Old Analysis**

This exploratory analysis will distinguish the effect of treatment with MIR RBCs versus REF RBCs when units were stored for  $\leq$  21 days. All MIR RBCs will be stored for  $\leq$  21 days; however, REF RBCs may be stored for up to 42 days. In this analysis, the primary endpoint of normalized Hb AUC will be analyzed similarly to the primary analysis, but all normalized Hb AUCs that resulted from REF RBCs stored longer than 21 days (at least 1 unit per transfusion is stored longer than 21 days) will be excluded. Note that the study is powered to assess the primary endpoint of MIR RBCs compared to REF RBCs administered per current standard of care which allows REF RBCs to be stored longer than 21 days. This analysis is exploratory and is not powered to determine non-inferiority.

### **Non-Irradiated RBC Only Analysis**

This exploratory analysis will be conducted to evaluate whether irradiation of REF RBCs has an impact on the primary treatment comparison. In this analysis, the primary endpoint of normalized Hb AUC will be analyzed similarly to the

primary analysis, but all normalized Hb AUCs that resulted from irradiated REF RBCs will be excluded.

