10.2 Red Blood Cell Products

The RBCs to be utilized in this study will be as follows and will meet standard release criteria for transfusion:

- MIR RBCs: RBCs will be derived from WB collected in CPD solution, treated with the Mirasol System for WB, LR, and stored in AS-3 for \leq 21 days at 1 - 6°C.
- REF RBCs: LR apheresis RBCs or WB-derived RBCs will be per site standard inventory.

No other pathogen reduction treated blood products including platelets and/or plasma may be used for transfusion in subjects during study participation.

MIR RBCs will be prepared from WB treated with the Mirasol System for WB according to the Blood Processing and Storage Guidelines and the Mirasol System for WB Illuminator Operator's Manual.

The MIR RBCs must not be irradiated. Irradiating blood products that have been Mirasol-treated is redundant and may further compromise RBC viability. In vitro studies demonstrated Mirasol treatment was as effective as irradiation in preventing leukocyte proliferation and was more effective than gamma irradiation at preventing antigen presentation, cytokine production, and T-cell activation.

Modifications such as RBC washing (MIR RBCs or REF RBCs) or irradiation (REF RBCs only) may be done according to Hospital Site and/or Local Blood Center standard procedures and following established guidelines as to impact to storage durations and transfusion practices. Any modifications will be captured in the electronic case report form (eCRF). Anticipated incidence of washing is 35% for conventional RBCs and 33% for irradiated RBCs.³⁰

Mirasol increases extracellular potassium in WB derived RBC products. Use with caution in patients at risk of hyperkalemia (eg, patients with renal failure) and/or requiring administration via central venous access device.

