## **V. Interventions**

### **A. Clinical Trial Material**

The RBCs to be utilized in this study will be as follows and will meet standard release criteria for transfusion.

- MIR RBCs: RBCs will be derived from WB collected in citrate phosphate dextrose (CPD) solution, treated with the Mirasol System for WB, LR, and stored in Additive Solution Formula 3 (AS-3) for  $\leq$  21 days at 1 - 6°C.
- REF RBCs: LR apheresis RBCs or WB-derived RBCs will be per site standard inventory.

No other pathogen reduction treated blood products including platelets and/or plasma may be used for transfusion in subjects during study participation.

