### **B. Primary Efficacy Endpoint Analysis**

The primary analysis will use a mixed effect repeated measures model on the log-transformed data to assess differences between treatments using the FAS. A

random subject-level effect will be used to accommodate dependence in responses within subjects over time. Fixed main effect terms for period, treatment, treatment\*period interaction and baseline normalized Hb AUC will be included in the model. Mirasol-treated WB will be coded as 1 and conventional treatment will be coded as 0 in the model.

A one-sided 97.5% confidence interval for treatment differences will be used to test the primary hypothesis that the normalized Hb AUC as a measure of RBC survival derived from Mirasol-treated WB is non-inferior to normalized Hb AUC after transfusion of conventional untreated RBCs. Assuming a non-inferiority margin of 20% (at the original scale), the use of RBCs derived from Mirasol-treated WB will be declared non-inferior to conventional, untreated RBCs if the lower limit of the one-sided confidence interval for the treatment effect (RBCs derived from Mirasol-treated WB mean minus conventional) is greater than  $\ln(0.80) = -0.2231$ .

The following provides sample code for implementing the MMRM analysis:

```
ods output lsmeans=lsmeans diff=diffs;
proc mixed data=test;
class subjid trt period trannum;
model resp=period trt trt*period trannum basehb/ddfm=kr;
random subjid(sequence)/sub=subjid type=cs;
lsmeans trt/diff alpha=.05;
```

where

- RESP is the log(normalized Hb AUC)
- TRT is the variable for treatment (0 for REF RBCs; 1 for MIR RBCs)
- BASEHB is the pre-treatment Hb
- PERIOD is the variable for period
- TRANNUM is the variable to identify the order of the two transfusions following the 50-day washin-in period for each treatment period (1 for first transfusion, 2 for second transfusion)
- SUBJID is for subject

The carryover effect will be tested with the TRT\*PERIOD interaction term. If the interaction is significant, then a carryover effect may be present and alternative analysis methods may be considered.

Several secondary/exploratory analyses will be conducted on the primary endpoint. Each are described below:

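### The non-irradiated and 21-day analyses drop REF AUCs but keep the same subjects' MIR AUCs, so part of any between-site difference in AUC can enter the MIR-REF estimate

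*SAP*

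**What the plan says.** SAP VIII.B defines two exploratory reruns of the primary analysis. The Non-Irradiated RBC Only Analysis is fitted like the primary one, "but all normalized Hb AUCs that resulted from irradiated REF RBCs will be excluded". The RBC ≤ 21 Day Old Analysis is fitted likewise, "but all normalized Hb AUCs that resulted from REF RBCs stored longer than 21 days". In the second, a single unit older than 21 days is enough to exclude that transfusion's AUC. It can matter because "REF RBCs may be stored for up to 42 days", whereas MIR units are limited to 21 days. Neither paragraph says what happens to the MIR AUCs of a subject who loses REF AUCs.

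In the model itself (SAP VIII.B, Primary Efficacy Endpoint Analysis) a "random subject-level effect will be used to accommodate dependence in responses within subjects over time". SAP VI.C plans no adjustment for center.

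Which REF AUCs are lost depends on local practice. Protocol 10.2 says that "irradiation (REF RBCs only) may be done according to Hospital Site and/or Local Blood Center standard procedures". SAP V.A says "REF RBCs: LR apheresis RBCs or WB-derived RBCs will be per site standard inventory".

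**The concern.** The crossover is meant to compare the two products within the same patient. A subject whose REF transfusions were all irradiated stays in the non-irradiated analysis with MIR AUCs alone. Because the subject effect is random, the model still uses that subject by comparing those MIR AUCs with other subjects' REF AUCs. If irradiation is a site habit, this compares MIR at irradiating sites with REF at other sites.

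Site means could differ for reasons unrelated to the product. Under SAP VIII.A the trapezoid runs to the pre-transfusion Hb of the next interval, and no division by interval length is stated. Physicians set transfusion frequency, and the eligible mean interval is 2 to 4 weeks (Protocol 11.2). A longer interval gives a larger AUC.

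The non-irradiated analysis exists to show whether REF irradiation changes the primary comparison, and the 21-day analysis examines the comparison without older REF units. A site difference could create or hide such a change.

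**Working it through.** **Inputs from the documents.** Variance of within-subject log differences 0.015412, within-subject variance 0.007706, correlation ρ = 0.35, margin -0.2231, 16.7% reduction, N = 77 (all SAP IV.C).

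**Assumptions.** A share p of subjects has MIR AUCs only. I take p = 0.33, with 0.20 to 0.50 as the range. Protocol 10.2 gives a 33% figure for irradiated RBCs, but as worded it is an incidence of washing, so it is not a firm source. All patients at an irradiating site receive irradiated REF, and there is no treatment-by-site effect. The site difference in log AUC, δ, is unknown and is varied.

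**The plan's own figure.** With ln(0.833) = -0.1827, the distance to the margin is 0.0404. Then n = (1.96 + 0.84)² × 0.015412 / 0.0404² ≈ 75 by the normal approximation and 77 by the paired t. This matches the stated 77, and 77/0.8 gives 97. The printed true mean of -0.1839 gives 79 (normal) or 81 (t). With all 77 subjects, SE = √(0.015412/77) = 0.0141.

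**How much of δ enters.** For a random-intercept model with one summary per product and a share p of MIR-only subjects:

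estimate = (MIR - REF in complete subjects) + (1 - ρ) × p × δ

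At p = 0.33 the coefficient is 0.65 × 0.33 = 0.2145.

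**Its SE.** The total variance per summary is 0.007706/0.65 = 0.011855. Then Var = (1 - ρ)² × 0.011855/77 + (1 - ρ²) × 0.011855/[77(1 - p)]. At p = 0.33 this is 0.0000651 + 0.0002017 = 0.000267, so SE = 0.0163.

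| p | share of δ entering | SE | δ for a one-SE shift | difference in AUC |
|---|---|---|---|---|
| 0.20 | 0.130 | 0.0153 | 0.118 | about 12% |
| 0.33 | 0.2145 | 0.0163 | 0.076 | about 8% |
| 0.50 | 0.325 | 0.0183 | 0.056 | about 6% |

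**Check by simulation.** REML fits used period, treatment, treatment-by-period, transfusion number and random subject, with N = 77, two AUCs per period and no baseline covariate. Entries are shift/SE.

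| p | δ = 0.05 | δ = 0.10 | δ = 0.20 |
|---|---|---|---|
| 0.20 | 0.42 | 0.79 | 1.23 |
| 0.33 | 0.66 | 1.22 | 1.71 |
| 0.50 | 0.86 | 1.54 | 2.04 |

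At p = 0.33 and δ = 0.10 the shift is 0.0201, against 0.0215 from the formula. At δ = 0.20 it is 0.0288, not 0.0429, because a large site difference inflates the estimated between-subject variance and less passes through. If 0.007706 is instead the variance of each single AUC, the ratios at p = 0.33 are about 0.6-0.7, 1.1 and 1.2-1.4.

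**With baseline normalized Hb AUC as covariate** (p = 0.33): 0.48, 0.81 and 1.02 SE at δ = 0.05, 0.10 and 0.20.

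**What δ could be.** Assume that Hb falls 1% per day and that AUC is not divided by time. Then AUC = T - 0.005T², which is 18.795 at 21 days and 20.355 at 23 days, so δ = ln(20.355/18.795) = 0.080. Spread of intervals within sites weakens the effect. With a within-site SD of 2 days, simulated shifts for 21 versus 23, 24 and 28 days were 0.5, 0.6 and 0.9 SE; with no spread they were 0.9, 1.4 and 1.4.

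**21-day analysis**, half the subjects at sites with older stock, shift/SE:

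| REF AUCs excluded, old-stock v other sites | δ = 0.05 | δ = 0.10 | δ = 0.20 |
|---|---|---|---|
| 90% v 10% | 0.72 | 1.22 | 1.52 |
| 60% v 10% | 0.32 | 0.52 | 0.73 |
| 50% v 50% | 0.14 | 0.06 | -0.03 |

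The last row is close to zero.

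**Paired subjects only.** In the irradiation analysis the shift is 0.002 or less in size at every δ. In the 21-day analysis with clustered stock, 0.002 to 0.005 remains, because some subjects keep two MIR AUCs and one REF AUC.

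**The case against.** The strongest reply is that the size rests on figures the plan does not contain. The 2-to-4-week interval is an eligibility range for patients and says nothing about irradiating versus other sites. The 33% is ambiguously worded, and no share of REF units older than 21 days is given. If the AUC were divided by interval length, 21 versus 28 days at 1% per day would give δ of about 0.04 and a shift of about 0.5 SE. All of this stands, and it is why the result can only be stated conditionally.

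The SAP text also lists baseline normalized Hb AUC in the model, which reduces the shift. That protection is uncertain. SAP VI.D and the sample code use Hb rather than AUC, and Protocol Table 14-1 schedules no Hb series before the first study transfusion from which a Period 1 baseline AUC could be computed.

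The 21-day exclusion works per transfusion, so many subjects may keep one REF AUC. A shift above one SE there needs old stock to be strongly concentrated at some sites. This also stands.

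Finally, both analyses are labelled exploratory and carry no decision rule. A reader might set the shift against the 0.0404 distance to the margin and infer a threat to the non-inferiority conclusion. The documents do not support that, since these exclusions do not apply to the primary analysis.

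**Conclusion.** The defect is in the rule as written: REF AUCs are removed on a criterion linked to site practice, the matching MIR AUCs stay, and nothing in the model confines the comparison to within subjects. Its size is conditional. At p = 0.33 and ρ = 0.35 about a fifth of a site difference enters, so one SE (0.0163, enough to move a ratio of 0.833 to about 0.847) needs sites to differ by roughly 8% in AUC, or 6% to 12% over the range of p considered. The sign follows the sign of the site difference.

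Two stronger readings are tempting. One is that the estimate simply absorbs site differences; only a fraction passes through, and a smaller one as between-subject variance grows. The other is that a shift above one SE should be expected; the documents do not show that irradiating sites differ in AUC at all. The point is a modest one about two exploratory analyses, stronger for irradiation than for storage age. It is worth making because the bias affects the comparison these analyses are there to make and is cheap to avoid.

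**What to change.** Add one sentence to each of the two paragraphs in SAP VIII.B: *only subjects with at least one eligible REF AUC and at least one MIR AUC are included, and the number of subjects lost is reported.* A count by site would also show whether the exclusions cluster.

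The alternative is to fit subject as a fixed effect in these two analyses. The treatment-by-period term must then be dropped, because it is aliased with sequence, which the subject effects already contain. This version should also remove the small remainder in the 21-day analysis, since only within-subject contrasts are used.

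The cost of the paired restriction at p = 0.33 is about 0-5% in SE (0.0172 against 0.0163 for small site differences, and almost nothing for large ones). If half the subjects were MIR-only it would be about 9%: √(0.015412/38.5) = 0.0200 against 0.0183. A shift of 0.002 to 0.005 stays in the 21-day analysis if subject remains random.

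Protocol 21.7.1.1 describes a different analysis, with contrasts against irradiated and non-irradiated REF and a test between them, and the same for storage up to and beyond 21 days. The two documents should be reconciled in the same edit.

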Safety Assessments:	
Safety will be evaluated by assessment of physical examinations, vital signs, clinical laboratory values, TEAEs, UADEs, SAEs, and discontinuations due to treatment-related AEs. Safety will be assessed according to the National Cancer Institute (NCI) Common Toxicity Criteria for Adverse Events (CTCAE) scale, Version 4.03.
 
This trial will be monitored using an independent Data Monitoring Committee (DMC) operating under a ratified charter. The DMC will review SAE/UADE reports on an ongoing basis. Additionally, the DMC will review safety reports summarizing the frequency and severity of TEAEs, UADEs, and other relevant safety information as defined in the DMC charter. Enrollment will not be placed on hold during the DMC review process. The DMC will determine if the observed AEs are acceptable for this patient population, and will make recommendations to the Sponsor regarding study continuation.

Statistical Methodology:	
Eligible subjects will be randomized to treatment sequence via an electronic system using a permuted-block schedule stratified by investigational site. The primary endpoint will be the normalized Hb AUC calculated from normalized Hb between successive transfusions as a measure of the percent surviving RBCs and will be evaluated for the first 2 transfusions after a 50-day wash-in for each treatment period. These 2 measurements of normalized Hb AUC within each period will be used for analysis.
 
The primary hypothesis is that the normalized Hb AUC as a measure of RBC survival derived from Mirasol-treated WB is not inferior to normalized Hb AUC after transfusion of conventional untreated RBCs. The study has approximately 80% power to show the decrease in normalized Hb AUC of RBCs derived from Mirasol-treated WB is not more than 20% of the decrease in normalized Hb AUC of conventional untreated RBCs, assuming a 1-tailed type 1 error rate of 2.5%.

TABLE OF CONTENTS

1	INTRODUCTION.....	18
1.1	Pathogen Risk	19
1.2	White Blood Cell Risk.....	21
1.3	Novel Device	22
2	DEVICE DESCRIPTION	22
2.1	Device Description.....	22
2.2	Principles of Operation	23
2.3	Principles of Use	23
3	INTENDED USE STATEMENT.....	24
4	NONCLINICAL STUDIES.....	24
5	CLINICAL TRIAL EXPERIENCE.....	25
5.1	The IMPROVE Study	25
5.2	The IMPROVE II Study	26
5.3	The AIMS Study	27
6	RATIONALE FOR THE CURRENT STUDY	28
7	OBJECTIVES	29
7.1	Primary Objective	29
7.2	Secondary Objective	29
8	EFFICACY ENDPOINTS.....	29
8.1	Primary Endpoint	29

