Sensitivity analysis will be performed to assess whether results of the primary efficacy analysis (based on treatment effect plus subject effect) are robust to the assumption of no carry over or period effects. The primary analysis of the primary efficacy endpoint will also be performed using the per protocol analysis set.

A secondary analysis will be conducted to evaluate whether irradiation of REF RBCs has an impact on the primary treatment comparison. This analysis will include a binary classification to identify REF RBC transfusions that utilized irradiated RBCs. Tests will then be carried out comparing the MIR RBCs to irradiated REF RBCs as well as MIR RBCs to non-irradiated REF RBCs, and a final test will compare these to treatment effects to assess whether they are statistically significantly different. Similar analyses will be conducted to evaluate the impact of older REF RBCs on the primary endpoint. This analysis will distinguish the effect of treatment with MIR RBCs versus REF RBCs when units were stored for ≤ 21 days and MIR RBCs versus REF RBCs stored when units were stored for > 21 days. Note that the study is powered to assess the primary endpoint of MIR RBCs compared to REF RBCs administered per current standard of care.

The frequency of off-protocol transfusions will be estimated during the run-in period and treatment periods for MIR and REF RBC products. This frequency will be estimated using generalized estimating equations with this binary response (on- versus off-protocol), a logistic link, a main effect for assigned treatment (MIR vs. REF RBCs), and an exchangeable correlation

matrix to accommodate the dependence within patients. The results of this descriptive analysis will give context to the intention-to-treat and per-protocol non-inferiority analyses.

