## C. Sample Size Estimation

Data from the IMPROVE II study were available to obtain information on normalized Hb AUC associated with RBCs derived from Mirasol-treated WB as well as from untreated WB. Pairwise differences in the natural log-transform of normalized Hb AUC from treatment and control were used to obtain estimates required for determining the sample size needed for this study.

The mean difference in log-transformed Hb AUC values suggests a reduction of 16.7% resulting from the use of MIR RBCs. The sample variance of within subject differences is 0.015412. The estimate of the within subject variance required for the 2x2 crossover design is one-half of the variance of within subject differences (0.007706).

The primary hypothesis is that RBCs derived from Mirasol-treated WB are not inferior to conventional, untreated RBCs with respect to normalized Hb AUC. Assuming a within subject variance of 0.007706 and a 16.7% reduction in normalized Hb AUC, approximately 77 subjects are needed to obtain at least 80% power to show the decrease in normalized Hb AUC from RBCs derived from Mirasol-treated WB is not more than 20% of the normalized Hb AUC from conventional untreated RBCs assuming a 1 tailed type 1 error rate of 2.5%. Algebraically if  $\ln(\mu_M)$  is the mean of the natural log-transformed Hb AUC for MIR RBCs and  $\ln(\mu_C)$  is the mean of the natural log-transformed Hb AUC for REF RBCs, the sample size is calculated to detect an alternative hypothesis versus a null hypothesis stated as:

$$H_0 : \ln(\mu_M) - \ln(\mu_C) \leq -22.3\% \text{ versus } H_a : \ln(\mu_M) - \ln(\mu_C) > -22.3\%$$

In the original scale (indicated by \*), the above hypotheses translate to:

$$H_0 : \frac{\mu_M^*}{\mu_C^*} \leq 0.80 \text{ versus } H_a : \frac{\mu_M^*}{\mu_C^*} > 0.80$$

Assuming a potential 20% discontinuation rate, approximately 97 patients may be enrolled.

The sample size was calculated using SAS 9.3 proc power for paired two samples t-test with option for finding difference with the null difference at the non-inferiority margin of -0.2231 (corresponding to 20% non-inferiority margin at the original scale), true mean of -0.1839 (corresponding to 16.7% observed

decrease in IMPROVE II), and correlation of 0.35. Should the correlation be higher, the proposed sample size will have higher power for the non-inferiority test.

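### The SAP keeps MIR versus non-irradiated and versus up-to-21-day REF, but omits the irradiated and over-21-day comparisons and the tests of difference that the protocol plans

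*SAP*

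**What the plan says.** Protocol 21.7.1.1 describes a secondary analysis with a binary flag for REF transfusions that used irradiated units: "Tests will then be carried out comparing the MIR RBCs to irradiated REF RBCs as well as MIR RBCs to non-irradiated REF RBCs". A last test then asks whether those two treatment effects differ. The same approach is promised for REF age, split at 21 days of storage.

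SAP VIII.B handles both questions by exclusion and labels both analyses exploratory. Its Non-Irradiated RBC Only Analysis still gives as its purpose to find out whether irradiation of REF affects the main comparison. Its method is to rerun the primary model, and "all normalized Hb AUCs that resulted from irradiated REF RBCs will be excluded". The RBC ≤ 21 Day Old Analysis is built alike; the rule for dropping a REF AUC reads in part "at least 1 unit per transfusion is stored longer than 21 days) will be excluded". The SAP does not mention or explain the change from the protocol.

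Exposure is one-sided by design. Protocol 10.2 forbids irradiating MIR and allows it for REF. The SAP notes that all MIR is stored for at most 21 days, while REF may be stored for up to 42.

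**The concern.** If irradiated or older REF units survive less well, REF as a whole performs worse and non-inferiority becomes easier to show. The protocol planned to measure that influence. An analysis that deletes the irradiated REF AUCs has no irradiated group left, so it can estimate neither MIR against irradiated REF nor the gap between the two kinds of REF. The same holds for REF stored over 21 days.

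The deletion also applies only to REF AUCs. Patients who lose theirs keep their MIR AUCs in the mixed model, so the restricted estimate partly draws on differences between patients.

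Elsewhere the SAP uses the right tool: its Region Analysis adds a region-by-treatment interaction. At stake is the reading of the primary result, not its validity, since the primary comparison is with REF as used in standard care.

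**Working it through.** **1. Plan against plan.**

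| Analysis | Protocol 21.7.1.1 | SAP VIII.B |
|---|---|---|
| MIR vs non-irradiated REF | yes | yes, by exclusion |
| MIR vs irradiated REF | yes | no |
| Test that the two differ | yes | no |
| MIR vs REF up to 21 days | yes | yes, by exclusion |
| MIR vs REF over 21 days | yes | no |
| Test that the two differ | yes (by the reference to similar analyses) | no |

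The storage rule states how an episode with mixed units is classed (one older unit is enough). The irradiation rule does not.

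**2. Planning inputs and the plan's own sample size.** From SAP IV.C: "The sample variance of within subject differences is 0.015412", so SD = √0.015412 = 0.1241; "null difference at the non-inferiority margin of -0.2231"; and "true mean of -0.1839". The protocol synopsis gives the error rate, "assuming a 1-tailed type 1 error rate of 2.5"%. Power is that of a one-sided paired t-test, with noncentrality δ√n / SD and n − 1 degrees of freedom.

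- True mean ln(0.833) = −0.1827 (the 16.7% reduction): δ = 0.2231 − 0.1827 = 0.0404. Power at 77 is about 80.5%, and N = 77.
- Printed mean −0.1839: δ = 0.2231 − 0.1839 = 0.0392. Power at 77 is 78.1%, and N = 81.
- Dropout: 77 / 0.80 = 96.25, hence 97.

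The statement that "approximately 77 subjects are needed to obtain at least 80% power" is therefore reproduced from the 16.7% figure. It concerns the primary test only. The distance from the planning effect to the margin is about 0.04 log units.

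**3. What the SAP's approach can reveal.** If a share p of REF is irradiated, the all-REF estimate and the non-irradiated-only estimate differ by about p times the true irradiated versus non-irradiated gap. Take an illustrative 10% deficit: −ln(0.90) = 0.1054. At p = 0.33 the visible shift is 0.33 × 0.1054 = 0.035. The SAP attaches no interval or test to it.

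**4. What the restored contrast can reveal.** Assume 77 patients, each with REF wholly irradiated or wholly not, and the SD above. Then SE = 0.1241 × √(1/n_irr + 1/n_non), the 95% half-width is 1.96 × SE, and the difference detectable at 80% power (two-sided 5%) is (1.960 + 0.842) × SE.

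| Share irradiated | n_irr / n_non | SE | Half-width | Detectable (log; %) | Power for 0.0392 | Shift seen under step 3 |
|---|---|---|---|---|---|---|
| 10% | 7.7 / 69.3 | 0.047 | 0.092 | 0.132; 14% | 13% | 0.011 |
| 20% | 15.4 / 61.6 | 0.035 | 0.069 | 0.099; 10% | 20% | 0.021 |
| 33% | 25.4 / 51.6 | 0.030 | 0.059 | 0.084; 9% | 26% | 0.035 |
| 50% | 38.5 / 38.5 | 0.028 | 0.056 | 0.079; 8% | 28% | 0.053 |

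The full contrast targets the whole 0.105 and comes with an interval; the SAP's comparison shows a fraction p of it with none. A difference equal to the planning distance to the margin would still usually be missed.

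**The case against.** The best defence is that the SAP keeps the comparisons that matter most. If the worry is a weakened comparator, MIR against non-irradiated REF and MIR against REF up to 21 days address it directly. The SAP calls both analyses exploratory and says that the storage-age one is not powered for non-inferiority. The restored contrast has low power and is not randomised: irradiation follows hospital and blood-centre procedure, so it may reflect site practice. The SAP is also written to protocol version 4.1 with an amendment pending, and the version of the protocol supplied is not visible, so a version difference cannot be ruled out.

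All of this stands. It limits the weight of the point but does not supply the missing estimate for the question that the SAP sets itself.

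A reader might infer more than the documents support:

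- **That the check has been removed and the SAP can show nothing.** Half of the planned comparisons remain, and restricted versus primary estimates give an indirect signal.
- **That the exclusion both costs a third of the pairs and leaves irradiated wash-in cells behind.** These need opposite assumptions. If irradiation is fixed by patient at 33%, about 52 pairs remain with 61–63% power, but patients classed as non-irradiated had no irradiated wash-in units. If it varies independently by episode, wash-in cells can carry over, but both AUCs are lost in only 0.33² = 11% of patients. About 69 pairs then remain, with 73–76% power.
- **That the protocol expects 33% of REF to be irradiated.** The sentence in Protocol 10.2 can be read as giving washing rates only. The share is therefore an assumption here, shown over 10–50%.
- **That irradiation is known to shorten survival.** Protocol Table 19-4 reports half-lives of 28.0 and 26.0 days, not significantly different, in 16 subjects.
- **That classing by the assessed transfusion is a departure by the SAP.** The protocol also flags transfusions. Under equal doses and linear survival of 60 to 120 days, the assessed transfusion supplies 21–62% of circulating transfused cells at 2- to 4-week intervals. That could justify a sensitivity analysis, but neither document plans a wash-in-inclusive classification.

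**Conclusion.** The point holds as a gap between protocol and SAP. The irradiated and over-21-day comparisons and both tests of difference are missing, without explanation. As a result the irradiation analysis yields no estimate or interval for the impact it is meant to evaluate. Under an assumed one-third share, the indirect route shows about a third of any true gap.

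The practical weight is modest. These are supportive analyses, the primary test is unaffected, and the restored contrast has about 26% power for a 0.039 log difference (13–28% over shares of 10–50%). Those figures assume 77 evaluable patients, irradiation constant within patient, and the planning SD from healthy volunteers.

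**What to change.** Before database lock, replace the irradiation refit in SAP VIII.B with one model on all AUCs:

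- Use the primary model with a three-level product factor: MIR, non-irradiated REF, irradiated REF. Equivalently, add an irradiated-REF indicator to the existing treatment term, which is the protocol's binary flag.
- Report MIR against each REF type, and the difference between the two effects, each with a 95% CI.
- Class an episode as irradiated if at least one unit was irradiated, in line with the SAP's storage rule.
- Do the same for REF stored up to and over 21 days.
- Label the contrasts supportive, low-powered and non-randomised, and report estimates with intervals rather than relying on p-values.

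If the sponsor prefers exclusion only, the SAP should record and justify the change from the protocol. Classification that also counts wash-in units is an optional sensitivity analysis.

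The cost is SAP wording and two models. Irradiation status and date are already recorded for each REF unit (Protocol 13.3). Storage age may be missing for some, because Table 13-1 asks for the REF collection date only where available. The SAP should say how those units are handled and report their number.
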